## 13.4 Potential Benefits

For all participants, the services provided to support antenatal and early newborn care may result in improved health-seeking behaviors. Those who initiate and adhere to daily oral PrEP could have the benefit of reduced HIV acquisition. From a broader perspective, however, the information learned from this study will help program managers and policymakers understand the feasibility of this intervention among pregnant, HIV-uninfected women in sub-Saharan Africa.

## 13.5 Potential Risks

### 13.5.1 Venipuncture

Venipuncture is sometimes associated with discomfort. Venipuncture may lead to discomfort, dizziness, bruising, swelling, and rarely, an infection at the venipuncture site.

### 13.5.2 HIV and STI Testing

Site will collect from women vaginal swabs or urine (*PrEP Comparison Component only*) for chlamydia and gonorrhea testing. Maternal participants may become embarrassed, worried, or anxious when completing their STI testing, HIV risk assessment and/or receiving HIV counseling. They also may become worried or anxious while waiting for their HIV and additional STI test results. Individuals who learn that they have an HIV infection or other STI may experience anxiety or depression related to their test results. Staff members will be trained to provide counseling following these tests, to provide the necessary information for future prevention (if negative) or for care and treatment (if positive).

### 13.5.3 Dual-Energy X-ray Absorptiometry Scan

Bone mineral density is measured by dual-energy x-ray absorptiometry (DXA) which involves exposure to radiation. For this protocol, a maternal DXA scan will be conducted for both Cohorts in the PrEP Comparison Component per [Appendices IIA](#) and [IIB](#) for a total radiation exposure of up to 1.36 mrem (0.22 mrem for each scan of the spine, 0.46 mrem for each scan of the hip). This is comparable to the dose of radiation received from naturally occurring sources over a two to three-day period at sea level (approximately 0.8 mrem per day).

For infant participants in both Cohorts of the PrEP Comparison Component, a DXA scan of the whole body is conducted at birth and a DXA scan of the lumbar spine is done at birth and study exit. Assuming that up to three attempts may be required to complete scans of the whole body and lumbar spine in infants who undergo DXA scans, the total radiation exposure will be a maximum

of 4.08 mrem (0.89 mrem for each scan of the whole body, 0.47 mrem for each scan of the spine). This is comparable to the dose of radiation received from naturally occurring sources over a five-day period at sea level. For both maternal and infant participants, the exposure to radiation associated with the DXA scans is well below limits set forth by the FDA in 21 CFR 361.1(b)(3).

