#### **6.14 Infant DXA Scans**

Infants in the PrEP Comparison Component will undergo DXA scans of the whole body and lumbar spine at their Birth Visit and of the lumbar spine Week 26 postpartum. Scans will be performed according to standardized procedures described in the study-specific MOP. Scan images will be transferred electronically for centralized reading and results will be transmitted electronically from the central readers to the Data Management Center (DMC). The centralized readings of all scans will be made available to the study sites after the last scan has been read centrally. However, if an infant experiences a bone fracture subsequent to his or her scan, the result of his or her scan will be provided to the site as soon as available.

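### The stated maximum infant DXA exposure of 4.08 mrem counts one lumbar-spine scan where the protocol schedules two; it is 5.49 mrem if three attempts are allowed at each scheduled scan

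*Protocol*

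**What the plan says.** Protocol Section 13.5.3 sets out infant DXA exposure in the PrEP Comparison Component in one paragraph.

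- **Schedule.** For the whole body, "a DXA scan of the whole body is conducted at birth". For the spine, "a DXA scan of the lumbar spine is done at birth and study exit".
- **Repeat allowance.** The total is built by "Assuming that up to three attempts may be required to complete scans of the whole body and lumbar spine in infants".
- **Total.** It is described as a maximum "of 4.08 mrem (0.89 mrem for each scan of the whole body, 0.47 mrem for each scan of the spine").
- **Lay equivalent.** The infant dose is said to be "comparable to the dose of radiation received from naturally occurring sources over a five-day period at sea level". The daily background rate appears in the maternal paragraph just before: "approximately 0.8 mrem per day".

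The second spine scan is confirmed elsewhere. Section 6.14 provides for scans of the whole body and "lumbar spine at their Birth Visit and of the lumbar spine Week 26 postpartum". The infant visit tables in Sections 6.2.2.1 (birth) and 6.2.2.3 (Week 26) and the schedule in Appendix IIC agree.

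For mothers, Section 13.5.3 gives a total of up to "1.36 mrem (0.22 mrem for each scan of the spine, 0.46 mrem for each scan of the hip"). Section 6.10 schedules the maternal scans at the Labor & Delivery Visit and at Week 26 postpartum.

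**The concern.** A figure offered as both the total and the maximum should cover every scan that the protocol schedules, with whatever repeats it allows. The infant figure appears to cover the birth scans only. The sentence introducing it includes a spine scan at study exit, but the total leaves no room for that scan once the birth allowance has been used.

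The figure sits in the human-subjects section. Section 13.2 requires ethics committees to determine the level of risk to children under 45 CFR 46 Subpart D. An upper bound on infant radiation is part of what they are given for that purpose, and the error makes it look slightly more favourable than the schedule supports. No endpoint, analysis, eligibility rule or monitoring trigger depends on it.

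**Working it through.** **Inputs**

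| Quantity | Value | Source |
|---|---|---|
| Whole-body dose per scan | 0.89 mrem | Protocol 13.5.3 |
| Spine dose per scan | 0.47 mrem | Protocol 13.5.3 |
| Attempts allowed | up to 3 | Protocol 13.5.3 |
| Whole-body scans scheduled | 1 (birth) | Protocol 13.5.3, 6.2.2.1, 6.14, Appendix IIC |
| Spine scans scheduled | 2 (birth; Week 26, study exit) | Protocol 13.5.3, 6.2.2.1, 6.2.2.3, 6.14, Appendix IIC |
| Background rate | about 0.8 mrem per day | Protocol 13.5.3 |

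**Step 1: reproduce the printed figure.** 3 × (0.89 + 0.47) = 3 × 1.36 = 4.08 mrem, an exact match. A search over whole numbers of exposures (0 to 9 whole-body, 0 to 14 spine) found that only three whole-body plus three spine exposures give 4.08. The stated equivalent follows from it: 4.08 / 0.8 = 5.1 days.

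**Step 2: check the counting convention on the maternal figure.** Two visits, one spine and one hip scan at each: 2 × (0.22 + 0.46) = 2 × 0.68 = 1.36 mrem, again exact. The maternal total therefore counts both visits. The agreement with the 1.36 in Step 1 is a coincidence: there it is the sum of one infant whole-body and one infant spine dose.

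**Step 3: recompute the infant total under each reading of the allowance.**

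| Reading | Formula | Total | Days at 0.8 mrem per day |
|---|---|---|---|
| No repeats, all scheduled scans | 0.89 + 2 × 0.47 | 1.83 mrem | 2.3 |
| At most three spine exposures across both visits | 3 × 0.89 + 3 × 0.47 | 4.08 mrem | 5.1 |
| Three attempts at birth, one spine exposure at exit | 3 × 0.89 + 4 × 0.47 | 4.55 mrem | 5.7 |
| Three attempts at each scheduled scan | 3 × 0.89 + 6 × 0.47 | 5.49 mrem | 6.9 |

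**Step 4: size of the difference.** Under three attempts at each scheduled scan, 5.49 − 4.08 = 1.41 mrem, which is the three exit spine attempts left out (3 × 0.47). The ratio is 5.49 / 4.08 = 1.35.

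**The case against.** The strongest reply is that the allowance is not worded as three attempts at each scheduled scan at each visit. It can be read as three exposures per scan type per infant, and then 4.08 mrem is exactly right. So 5.49 mrem is not a number the protocol commits to. A reader might infer that the protocol's own figures fix the maximum at 5.49; they do so only if the allowance applies to each scheduled scan. That part of the reply stands.

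The reply does not rescue the text as printed. The cap is nowhere stated. It would allow two repeats for the single whole-body scan but only one repeat shared between two spine scans about six months apart. If three spine attempts were used at birth, it would leave none for the scheduled exit scan; performing that scan once brings the total to 4.55 mrem.

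Two further points are fair. The background equivalents are loose: the maternal 1.36 mrem is 1.7 days at the stated rate, but the text says two to three days. The infant day count should therefore be treated as a consequence of the scan count, not as a separate error. Ethics committees can also see the per-scan doses and both time points in the same paragraph, so nothing is concealed.

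**Conclusion.** Wrong as written, and minor. The printed maximum matches three attempts at the birth scans alone and omits the exit spine scan that its own paragraph schedules. Applying the three-attempt allowance to each scheduled scan gives 5.49 mrem, about 35% above the printed figure and about seven days of background. With repeats at birth only, it is 4.55 mrem. The figure of 4.08 mrem is a true maximum only under an unstated cap of three spine exposures across both visits. These results rest on the protocol's per-scan doses and its 0.8 mrem daily rate, taken at face value.

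Two stronger inferences are not supported. A reader might conclude that the statement about FDA limits fails. The protocol gives no numeric limit against which to test it, and nothing here contradicts it. A reader might also assume that the same figure is repeated in the consent forms. Those pages were not available for this review, so that cannot be said either way.

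**What to change.** Reconcile the scan schedule, the attempt allowance and the stated total in Section 13.5.3. Either course would do:

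- Restate the maximum and its background equivalent so that they cover every scheduled scan. With three attempts at each scheduled scan, that is 5.49 mrem and about seven days.
- State explicitly the cap on attempts under which the printed total is a true maximum. With at most three spine exposures per infant across both visits, 4.08 mrem and five days can stand, and only the clarifying words are new.

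Which allowance applies is for the sponsor to say. The cost is a sentence of risk text. On the first course the figure becomes slightly less favourable. Neither course requires a change to an endpoint, the analysis or the visit schedule.

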#### **13.5.4 PrEP (FTC/TDF)**

FTC/TDF may have side effects, some of which are listed below. This list includes the more serious or common side effects with known or possible relationship. Maternal participants taking FTC/TDF will be monitored closely for any side effects, and are asked to report all side effects to the study site clinician. Refer to [Section 1.3.2](#) for information of the safety of PrEP during pregnancy and breastfeeding.

The following side effects have been commonly associated with the use of FTC/ TDF as treatment in HIV-infected adults:

- Gastrointestinal intolerance (such as nausea, abdominal pain, diarrhea, or vomiting), most commonly in the first month and typically resolves without treatment
- Flatulence (gas), most commonly in the first month and typically resolves without treatment
- Headache, dizziness, tiredness, or inability to sleep

Rare, but serious side effects include:

- Rash
- Worsening or new kidney damage
- Bone pain and bone changes such as thinning and softening
- Allergic reaction
- Lactic acidosis (buildup of too much acid in the body). Lactic acidosis can cause shortness of breath, nausea and liver failure.
- Depression and unusual dreams have been reported in HIV infected persons taking Truvada

#### **13.5.5 HIV Resistance**

It is possible that a maternal participant who is taking PrEP and becomes infected with HIV during this study may develop resistance to FTC/TDF. Multiple steps will be taken to minimize the risk of drug resistance. HIV testing will be performed frequently throughout follow-up for all maternal participants. If acute HIV infection is suspected after enrollment for any participant accepting PrEP, the participant will undergo evaluation using tests described in [Appendix IID](#). These steps should minimize the risk of drug resistance occurrence by identifying HIV infection in its early stages and stopping study drug. If a participant becomes infected during the study, real-time resistance testing will be conducted for clinical management (see [Section 6.3](#)).

#### **13.5.6 Sensitive Questions**

Maternal participants will be asked questions about their sexual behavior that may make them feel uneasy. Maternal participants do not have to answer any question that they do not want to and can stop answering the questions at any time.

### **13.5.7 Mobile Phones**

As described in [Section 3.2](#), all maternal participants enrolled in the PrEP Comparison Component will receive SMS texts on antenatal, delivery, and early infant care, and maternal participants in Cohort 1 will also participate in SMS messaging to promote PrEP adherence. It is possible that timing or volume of text messages will be inconvenient to maternal participants. Because the costs for text messaging will be covered by the project, it should not incur additional expense for the maternal participant.

Information entered by maternal participants into mobile phone programs will be maintained on a 21CFR Part 11 compliant secure server via a secure, password-protected log-in. However, it is possible that someone who has access to the maternal participant's phone may see this information, revealing participation in the study. It will not be possible for the study team to access any private information on maternal participants' mobile phones. Lost or stolen phones are a practical reality. Maternal participants will be trained to secure their phones with a password or PIN and to delete old messages. Messages will not disclose individual level information so that if accessed will not compromise confidentiality around health status or medication use.

### **13.6 Potential Social Impact**

Participation in clinical research includes the risk of loss of confidentiality. Although study sites make every effort to protect participant privacy and confidentiality, it is possible that participants' involvement in the study could become known to others, and that social harms – non-medical adverse consequences – may result (e.g., because participants could be perceived as being HIV-infected or at "high risk" for HIV infection, or because a participant's choice to participate or use PrEP is not supported). For example, participants could be treated unfairly, or could have problems being accepted by their families and/or communities or could experience problems in their relationships with their partner(s). The Protocol Team believes this risk is small, given that the target population is HIV-uninfected women; however, study staff will work to minimize such potential risks both at the clinic and community levels.

At every follow-up visit in the PrEP Comparison Component, sites will assess for social harms experienced since the last visit. All reported social harms will be source documented and entered into eCRFs for maternal participants. As part of routine study monitoring, social harms will be tabulated and reviewed as described in [Sections 7.2](#) and [9.3.2](#). In the event that a participant reports a social harm, every effort will be made by study staff to provide appropriate follow-up support and counseling to the participant as necessary; referrals to appropriate non-study resources may also be provided. Each site will provide such support in accordance with local standards of care and site SOPs.

### **13.7 Reimbursement/Compensation**

Pending IRB/EC approval, maternal participants will be reimbursed for costs associated with completing study visits (e.g., transport costs). Reimbursement amounts will be specified in site-specific ICFs or other materials if applicable per IRB/EC policies and procedures.

### **13.8 Privacy and Confidentiality**

All study procedures will be conducted in private and every effort will be made to protect participant privacy and confidentiality to the extent possible. Participant information will not be

released without written permission to do so except as necessary for review, monitoring, and/or auditing as described in [Section 11.2](#).

All study-related information will be stored securely. Participant research records will be stored in locked areas with access limited to study staff. Participant information necessary for implementation of the mHealth component (SMS messages), such as names and phone numbers, will be maintained on a General Data Protection Regulation (GDPR) compliant cloud server. All laboratory specimens, eCRFs, and other documents that may be transmitted off-site (e.g., EAE report forms, photographs of observed reactions, SMS message logs) will be identified by PID only. Likewise, communications between study staff and Protocol Team members regarding individual participants will identify participants by PID only.

Study sites are encouraged but not required by DAIDS policies to store study records that bear participant names or other personal identifiers separately from records identified by PID. All local databases must be secured with password protected access systems. Lists, logbooks, appointment books, and any other documents that link PID numbers to personal identifying information should be stored in a separate, locked location in an area with limited access.

### **13.9 Communicable Disease Reporting**

Study staff will comply with local requirements to report communicable diseases including HIV infection identified among study participants to health authorities. Participants will be made aware of all applicable reporting requirements as part of the study informed consent process.

### **13.10 Management of Incidental Findings**

Site clinicians will inform maternal participants (or other authorized guardians if applicable) of all clinically meaningful physical exam findings and laboratory test results, including results of HIV tests and hematology and chemistry tests. When applicable, site clinicians will provide referrals to non-study sources of medical care for further evaluation and/or treatment of these findings.

The results of protocol-specified DXA scans for infants are not planned to be provided to maternal participants, as there are no normal values for this test in infants and it is not expected to be relevant to clinical care and management. If, however, new information becomes available during the course of the study indicating that the results of the DXA scan are of clinical relevance, the results of this test will be provided prior to study exit.

### **13.11 Management of New Information Pertinent to Study Participation**

Maternal participants will be provided any new information learned over the course of the study that may affect their willingness to continue receiving study drug, their decision to take up PrEP and/or remain in follow-up in the study.

### **13.12 Post-Trial Access to Study Drug**

Maternal participants who choose to continue PrEP after exiting the study will be referred to appropriate non-study PrEP programs, if available, for continued services. If a PrEP program is not in place, maternal participants will be required to stop PrEP at the end of the study period. Participants will be counseled and referred to all HIV prevention methods available, outside of

the study, consistent with local standards of care. Each site will be required to engage applicable stakeholders and outline locally relevant procedures.

## **14 ADMINISTRATIVE PROCEDURES**

### **14.1 Regulatory Oversight**

This study is sponsored by the National Institute of Allergy and Infectious Diseases (NIAID), *Eunice Kennedy Shriver* National Institute of Child Health and Human Development (NICHD), and National Institute of Mental Health (NIMH), which are part of the United States National Institutes of Health (NIH). Study drug FTC/TDF is provided by Gilead Sciences, Inc.; however, this organization is not involved in sponsorship or regulatory oversight of this study.

The Division of AIDS (DAIDS) within the NIAID is responsible for regulatory oversight of this study. DAIDS will distribute safety-related information pertaining to the study drug prior to and during the conduct of the study, in accordance with its sponsor obligations.

NIAID provides funding to the clinical research sites at which this study will be conducted and contracts with independent clinical site monitors who will perform monitoring visits as described in [Section 12](#). As part of these visits, monitors will inspect study-related documentation to ensure compliance with all applicable U.S. and local regulatory requirements.

### **14.2 Protocol Registration**

Prior to implementation of this protocol, and any subsequent full version amendments, each site must have the protocol and the protocol ICFs approved, as appropriate, by their local IRB/EC, local IBC, and any other applicable regulatory entity. Upon receiving final approval, sites will submit all required protocol registration documents to the DAIDS PRO at the RSC. The DAIDS PRO will review the submitted protocol registration packet to ensure that all required documents have been received.

Site-specific ICFs will be reviewed and approved by the DAIDS PRO and sites will receive an Initial Registration Notification from the DAIDS PRO that indicates successful completion of the protocol registration process. A copy of the Initial Registration Notification should be retained in the site's regulatory files.

For any future protocol amendments, upon receiving final IRB/EC and any other applicable regulatory entity approvals, sites should implement the amendment immediately. Sites are required to submit an amendment registration packet to the DAIDS PRO at the RSC. The DAIDS PRO will review the submitted protocol registration packet to ensure that all the required documents have been received. Site-specific ICFs will not be reviewed and approved by the DAIDS PRO and sites will receive an Amendment Registration Notification when the DAIDS PRO receives a complete registration packet. A copy of the Amendment Registration Notification should be retained in the site's regulatory files.

For additional information on the protocol registration process and specific documents required for initial and amendment registrations, refer to the current version of the DAIDS Protocol Registration Manual, which is available at: <https://www.niaid.nih.gov/research/daids-clinical-site-implementation-operations>

## **14.3 Study Implementation**

This study will be conducted in accordance with the protocol, international good clinical practice guidelines, and all applicable US and local regulations. Study implementation will also be guided by the IMPAACT MOP, study-specific MOP, LPC, and other study implementation materials, which will be available on the IMPAACT web site: [www.impaactnetwork.org](http://www.impaactnetwork.org).

Study implementation at each site will also be guided by site-specific SOPs. The DAIDS policy on *Requirements for Manual of Operations* specifies the minimum set of SOPs that must be established at sites conducting DAIDS funded and/or sponsored clinical trials (available on the website referenced in [Section 11.2](#)). These SOPs should be updated and/or supplemented as needed to describe roles, responsibilities, and procedures for this study.

